## 10.2. DATA ANALYSIS

### 10.2.1 QUANTITATIVE ANALYSIS

Available outcome data will be analysed on an intention to treat basis. Potential clustering of outcomes at the level of community hospitals will be accounted for using mixed-effects models. Adjustment for baseline imbalances in outcomes or relevant covariates will be considered as appropriate. Effects of variations in intervention uptake and other relevant effect modifiers will be explored.

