#### 4.1.1 STUDY OUTCOME MEASURES

The study outcomes are:

- i. A difference in trial arms at one-year follow-up in HbA1c (co-primary outcome 1)
- ii. A difference in trial aims at one-year follow-up in total cardiovascular risk (co-primary outcome 2)

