## 8. ASSESSMENT AND FOLLOW-UP

Each participant will be involved in the study for a minimum of 12 months after taking consent and baseline data. However, there may be a delay in contacting and scheduling participants for follow ups therefore, this may be slightly longer. The study is expected to start October 2018 and finish September 2021.

a. Questionnaire data will be collected by field workers via in-person interview for the full sample at baseline, 6 and 12 months at the community hospital where they were recruited (Table 1). A custom-designed form linked to Microsoft Access will be used to collect, validate, verify, and store respondents' data where possible or else data will be collected via paper forms and double-entered into the databases. All data files and databases will be password protected.

b. Biological samples. Blood samples will be collected from participants at baseline, 6 and 12 months, to measure Blood glucose, HbA1c and lipids, coordinating where possible with the annual routine tests offered to patients to reduce duplication. Blood will be drawn by a trained phlebotomist when participants come for interview and sent to laboratory for analysis. Data will be linked to the participant information using a unique respondent ID, which will be assigned to all study participants.

c. Interviews. During intervention development and qualitative evaluation, a subset of participants will be followed up using in-depth interviews and focus group discussions. These will be recorded on digital Dictaphones, with recordings initially stored on a personal computer or laptop in an encrypted folder with password protection. Recordings will be transcribed by professional transcribers conditional on signing of confidentiality and nondisclosure agreements.

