### 9.1. SAMPLE SIZE CALCULATION

This study was powered to detect a clinically important difference of 0.6 units HbA1c (SD 1.5 units) between the control and intervention arms. We required 693 participants from 21 hospitals (7 per arm) to achieve 80% power at 2.5% significance level (to account for multiple testing), assuming an ICC between hospitals of 0.02 and loss to follow-up rate of 20%.

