### 9.2. FORMAT AND SCALE OF THE DATA

Data will be collected from approximately 693 individuals newly diagnosed with diabetes, across 21 primary care units in the Chiang Mai and Lampang province of Thailand.

The following data will be collected at baseline, 6 months and 12 months:

- a. Questionnaire and body measurement data will be collected in person and entered where possible directly into a password-protected Microsoft Access database (via a form) on laptops, or else using double-entered paper forms.
- b. Blood samples will be labelled and sent for analysis at the local hospital lab, and once analysed the results will be merged back into the main database. Once fully entered and validated, data will be transferred to comma separated value (csv) files for more efficient long-term storage and sharing
- c. Qualitative data will be collected via interview and direct observation, and initially stored as voice and video recordings, later transcribed and data extracted using NVivo software.

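### Section 10.2.1 leaves adjustment for baseline HbA1c to depend on observed imbalance, and says nothing about missing 12-month values or the 6-month HbA1c; always adjusting would gain precision at no cost

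*Combined protocol and SAP*

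**What the plan says.** Section 10.2.1 of the protocol is the only place that describes the quantitative analysis. On the analysis set: "Available outcome data will be analysed on an intention to treat basis". On the model: "Potential clustering of outcomes at the level of community hospitals will be accounted for using mixed-effects models". On covariates: "Adjustment for baseline imbalances in outcomes or relevant covariates will be considered as appropriate". A last sentence plans to explore uptake and effect modifiers.

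Section 4.1.1 sets HbA1c at one year as the first co-primary outcome and total cardiovascular risk at one year as the second. Section 8 schedules the measurements: "Blood samples will be collected from participants at baseline, 6 and 12 months", HbA1c among them. Section 9.1 assumes a "loss to follow-up rate of 20" per cent and allows for it by recruiting more people. Sections 6.5 and 8.1 describe continued follow-up after withdrawal from the intervention, use of medical records with permission, reminders, calls and home visits. No section says what part the 6-month HbA1c plays in the analysis, how values still missing are treated, or on what assumption.

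**The concern.** Three things are left open.

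- **When adjustment is decided.** It is tied to imbalance, so the choice comes after baseline data have been seen. The trial is unblinded (section 4.1) and has seven units per arm, where chance imbalance is likely. The primary estimate can then depend on a judgement made late.
- **Precision.** Baseline HbA1c is usually the best available predictor of later HbA1c. Leaving it out discards information already paid for.
- **Missing 12-month values.** An analysis of available values with no covariates is unbiased only if dropout unrelated to HbA1c, or dropout alike in mechanism and rate across arms, can be assumed. The plan does not say which assumption it makes.

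At stake are some power, protection against a data-driven choice of model, and some robustness if dropout turns out to be selective.

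**Working it through.** **Inputs from section 9.1:** difference 0.6, SD 1.5, 2.5% level, 80% power, 7 units per arm, ICC 0.02, 20% loss. Sidedness is not stated; two-sided reproduces the plan's total, one-sided gives 525.

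**Assumed, not in the documents:** correlations between visits (baseline/6, baseline/12, 6/12 months) of 0.5/0.5/0.7, with a range from 0.3/0.3/0.5 to 0.7/0.7/0.8; and the dropout patterns in step 4.

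**1. The plan's own figure.**
Per arm before clustering: n = 2 × 1.5² × (2.241 + 0.842)² / 0.6² = 118.8, so 119.
Analysed per unit: n(1 − ICC)/(k − n × ICC) = 119 × 0.98 / (7 − 2.38) = 25.2, so 26.
Recruited per unit: 26/0.8 = 32.5, so 33. Total: 33 × 21 = 693, as stated.
The formula has no baseline-correlation term, so 693 is sized for an unadjusted comparison.

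**2. Unadjusted 12-month comparison.**
Between-unit variance 0.02 × 2.25 = 0.045; within-unit 0.98 × 2.25 = 2.205.
SE = √[2 × (0.045/7 + 2.205/(7 × 26))] = 0.193.
Power = Φ(0.6/0.1926 − 2.241) = Φ(0.874) = 80.9%.

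**3. Baseline-adjusted comparison.** Adjustment multiplies within-unit variance by 1 − ρ², where ρ is the baseline-to-12-month correlation. Between-unit variance may shrink by the same factor or not at all, so both cases are shown. At ρ = 0.5 with both shrinking, SE = 0.1926 × √0.75 = 0.167 and power = Φ(0.6/0.1668 − 2.241) = 91.2%. With only within-unit variance shrinking, SE = √[2 × (0.045/7 + 1.654/182)] = 0.176 and power is 87.8%. The last column replaces the normal reference by t on 12 degrees of freedom (14 units in a two-arm comparison, less 2).

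| Analysis | ρ | SE | Power, normal | Power, t on 12 df |
|---|---|---|---|---|
| Unadjusted | – | 0.193 | 80.9% | 70.6% |
| Adjusted, both shrink | 0.3 | 0.184 | 84.7% | 75.0% |
| | 0.5 | 0.167 | 91.2% | 83.4% |
| | 0.7 | 0.138 | 98.3% | 95.0% |
| Adjusted, within only | 0.3 | 0.187 | 83.4% | 73.5% |
| | 0.5 | 0.176 | 87.8% | 78.8% |
| | 0.7 | 0.159 | 93.8% | 87.0% |

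**4. Bias under assumed selective dropout.** Simulation with 2,000,000 participants per arm and 20% loss in each arm. In one arm dropout rises with 6-month HbA1c (odds ratio 1.5 to 2 per SD); in the other it is random.

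| Correlations | Unadjusted | Baseline-adjusted |
|---|---|---|
| 0.3/0.3/0.5 | 0.06–0.10 | 0.05–0.08 |
| 0.5/0.5/0.7 | 0.08–0.14 | 0.05–0.09 |
| 0.7/0.7/0.8 | 0.09–0.16 | 0.04–0.06 |

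If people with high HbA1c leave a DSME arm, the bias flatters DSME. With the same mechanism in both arms but 25% against 15% loss, at the middle correlations, it is 0.04–0.07 unadjusted and 0.03–0.04 adjusted. With the same mechanism and rate it is 0.00.

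**5. What the 6-month value adds.** Under the one-arm pattern and middle correlations, a longitudinal model with unstructured covariance leaves a bias of about 0.00 if everyone lost has a 6-month value, 0.02–0.04 if half do, and no improvement on baseline adjustment if none do. Its gain in power is about one point (91% to 92%, both variances shrinking). If dropout depends on the unseen 12-month value and half of those lost have a 6-month value, bias remains under every method: 0.12–0.19 unadjusted, 0.09–0.14 adjusted, 0.07–0.12 longitudinal.

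**6. Form of the longitudinal model.** In 500 simulated three-arm trials without selective dropout, a single unit intercept understated the SE (0.137 against a true 0.163; 4.0% rejection at a nominal 2.5%). Adding unit-by-visit effects corrected this (0.158 against 0.162; 2.0%; simulation error about 0.7 points).

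**The case against.** The strongest reply is that section 10.2.1 is brief, not wrong. It names adjustment for baseline imbalance in outcomes, and available data with mixed-effects models could include a longitudinal, baseline-adjusted analysis. That stands in part: a reader might infer that the plan requires an unadjusted, 12-month-only comparison, and it does not. But the mixed model is tied only to hospital clustering and adjustment only to imbalance, so that comparison is allowed and no alternative is fixed.

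A reader might also infer that the trial falls short of its power without adjustment. It does not by its own method: the normal approximation gives 80.9%. The 71% with t on 12 degrees of freedom reflects the small number of units and is not caused by leaving out baseline.

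Nor do the documents show that the result will be biased. They do not establish selective dropout, the retention steps in sections 6.5 and 8.1 limit it, and every odds ratio and correlation used here is assumed. Those steps reduce missing values without saying how the remainder are analysed.

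Finally, a full longitudinal model may be hard to fit with 21 units and an ICC of 0.02, and it adds little power. That stands, and is why it is offered as an option.

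**Conclusion.** The point holds as a free improvement to an under-specified analysis. Making adjustment unconditional removes a decision that would otherwise follow sight of the baseline data. It raises power from about 81% to 83–98%, depending on the assumed correlation (0.3 to 0.7) and on whether between-unit variance also shrinks. With t on 12 degrees of freedom the change is from about 71% to between 74% and 95%. Power rises at every value tried. Since the stated 80% is already met under the plan's approximation, the loss is of efficiency and not of the target.

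The bias argument is secondary and conditional. It needs HbA1c-related dropout that differs between arms in mechanism or rate. Under the one-arm pattern the bias is below one standard error and well below 0.6. Baseline adjustment reduces it but does not remove it.

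Total cardiovascular risk has the same gap in the text. No figures are claimed for it, because section 4.1.1 defines neither the score nor its scale.

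**What to change.** In section 10.2.1, before outcome data are examined:

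- Replace the conditional sentence with one primary analysis: a mixed model for 12-month HbA1c that always adjusts for baseline HbA1c, with a random effect for the randomised unit.
- State the missing-at-random assumption and what it is conditional on (arm and baseline HbA1c, plus the 6-month value if that is used).
- Add one sensitivity analysis for dropout that depends on the unseen 12-month value. One form shifts missing values in the DSME arms by a range of amounts and reports the shift at which the conclusion changes. At 20% loss a shift of 0.6 moves the contrast by 0.2 × 0.6 = 0.12. The team should choose and justify the range.
- Optionally, model baseline, 6- and 12-month HbA1c together, with unstructured within-participant covariance and both unit and unit-by-visit effects. Name the baseline-adjusted analysis as the fallback if the model does not converge.
- For total cardiovascular risk, always adjust for its baseline value on a scale suited to the score, and state how missing values are handled.

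The cost is a few sentences and slightly more modelling. The measurements are already scheduled, so no visits or participants are added. None of this helps much with people lost before 6 months, and only the sensitivity analysis addresses dropout driven by unseen values.

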## 5. RANDOMISATION

Twenty-one primary care units will be randomized (7 each) to provide nurse-led DSME, peer-led DSME, or standard care (1:1:1). Randomisation will be minimised by primary care networks to account for any variation in practice, although this is expected to be small because it is determined by the tertiary care hospital, which is same for both. The nurses and village health volunteers in intervention arms will be trained to deliver the intervention (at the community hospital or neighbourhoods as appropriate) using training films. No changes will be made to standard care, which currently involves a brief didactic educational session at the time of diagnosis of diabetes. While diabetes is diagnosed at tertiary hospitals, it is managed at, which are served by a full-time nurse (doctor visits weekly), and 10-15 village health volunteers linking patients in the community.

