The intervention will be evaluated in primary care networks in Chiang Mai and Lampang province in northern Thailand. While diabetes is diagnosed at tertiary hospitals, it is managed at community hospitals and health centres, which are served by a full-time nurse (doctor visits weekly), and 10-15 village health volunteers linking patients in the community. A 3-arm cluster randomized trial with inbuilt process and economic evaluation will be carried out (see Annexe for trial flow diagram). The 21 primary care units will be randomized (seven each) to provide nurse-led DSME, peer-led DSME, or standard care. Randomisation will be minimised by primary care networks to account for any variation in practice, although this is expected to be small because it is determined by the tertiary care hospital, which is same for both. The nurses and village health volunteers in intervention arms will be trained to deliver the intervention (at the community hospital or neighbourhoods as appropriate) using training films. No changes will be made to standard care, which currently involves a brief didactic educational session at the time of diagnosis of diabetes. Process evaluation will aim to assess intervention delivery (fidelity, dose and reach), clarify causal mechanisms (those hypothesised by theory of change developed within the project or identify unexpected ones), and identify contextual factors (barriers, facilitators) associated with variation in outcomes. Data for economic evaluation (resource usage and quality of life using EQ-5D) will be obtained prospectively alongside the trial.

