## 11.2 CONSENT

As this is a cluster-randomised study, consent to randomisation is obtained at the cluster (hospital) level. Informed consent will be obtained for procedures that are specifically for the purposes of the study, i.e. data collection and blood tests for adults newly diagnosed with diabetes and for those with poor control within three years after diagnosis. Consent to enter the study must be sought from each participant only after a full explanation has been given, an information leaflet offered, and time allowed for consideration. The PI is responsible for ensuring that all vulnerable participants are protected and participate voluntarily in an environment free from coercion or undue influence. All information sheets and consent forms will be available in English and Thai and will be verified for accuracy through back-translation. Consent discussions will be conducted in the appropriate language and a translator will be used if necessary.

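### The outcome models should name the 21 randomised units as clusters, include the minimisation factor and state small-sample inference; the hospital/unit difference itself is probably only naming

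*Combined protocol and SAP*

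**What the plan says.** **Allocation.** Section 5 states: "Twenty-one primary care units will be randomized (7 each) to provide nurse-led DSME, peer-led DSME, or standard care (1:1:1". Sections 4.1 and 7.1 (WP 3) say the same. Sections 5 and 7.1 add that allocation is minimised by primary care network, and that variation in practice between networks is expected to be small.

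**Analysis.** Section 10.2.1 is the only quantitative analysis text. On clustering it says: "Potential clustering of outcomes at the level of community hospitals will be accounted for using mixed-effects models". Adjustment for baseline imbalance or relevant covariates is left to be considered. The section mentions neither network nor any method of inference suited to few clusters.

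**Other names for the cluster.**
- Section 9.1: "We required 693 participants from 21 hospitals (7 per arm) to achieve 80% power at 2.5% significance level", "assuming an ICC between hospitals of 0.02 and loss to follow-up rate of 20" per cent.
- Section 11.2: "consent to randomisation is obtained at the cluster (hospital) level".
- Section 6.1 recruits at 21 hospitals; Section 6 recruits at 21 primary units.
- Section 8 assesses each participant at the community hospital of recruitment.
- Section 7.1, on where diabetes care takes place: "it is managed at community hospitals and health centres".

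**The concern.** In a cluster trial the arm contrast has to be judged against variation between the randomised clusters. If the random effect sits at a coarser level, some between-unit variance is treated as individual noise, intervals become too narrow and the error rate exceeds 2.5%. The analysis section and the randomisation section use different names for the cluster, and Section 7.1 mentions health centres beside community hospitals, so the level needs checking.

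Two further matters bear on the same sentence and do not depend on how the names are read. A factor used to balance the allocation normally belongs in the model. And with seven clusters per arm, a large-sample test understates the uncertainty in the between-cluster variance. Because the trial is unblinded, these choices are better fixed in advance than made once results are visible.

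**Working it through.** **1. Do the two names mean the same sites?**

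| Section | Term | Number |
|---|---|---|
| 4.1, 5, 7.1 | primary care units (randomised) | 21, seven per arm |
| 6 | primary units (recruiting) | 21 |
| 6.1 | hospitals (recruiting) | 21 |
| 9.1 | hospitals (sample size) | 21, seven per arm |
| 11.2 | hospital (cluster consenting to randomisation) | – |
| 8 | community hospital (recruitment and assessment site) | – |

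The count and the split by arm agree under both names, and Section 11.2 equates cluster with hospital. Nothing places several units under one hospital. The identity is implied but never stated.

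**2. The plan's own figure.** Inputs from Section 9.1: difference 0.6, SD 1.5, power 80%, significance level 2.5%, ICC 0.02, 7 clusters per arm, 20% loss. Sidedness is not stated; two-sided is assumed here.

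- Per arm, ignoring clustering: n = 2 × [1.5 × (2.2414 + 0.8416) / 0.6]² = 118.8.
- Analysed per cluster: m = n(1 − ICC) / (k − n × ICC) = 118.8 × 0.98 / (7 − 118.8 × 0.02) = 25.18, rounded up to 26.
- Recruited per cluster: 26 / 0.8 = 32.5, rounded up to 33.
- Total: 33 × 21 = 693, an exact match.

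The same steps with a one-sided 2.5% level give 525, so two-sided 2.5% is the version that fits. The match confirms that 21 clusters were assumed. It does not by itself show what those clusters are.

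**3. If the levels did differ (hypothetical).** Analysed per unit: 693 × 0.8 / 21 = 26.4.

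- Design effect: 1 + (26.4 − 1) × 0.02 = 1.508, with square root 1.228.
- If the model captured none of the unit variance, the effective critical value would be 2.2414 / 1.228 = 1.825, and the two-sided error 2 × [1 − Φ(1.825)] = 6.8%.
- Assumed ICC range: 4.5% at 0.01 (design effect 1.254) and 13.7% at 0.05 (design effect 2.27).

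If each unit is one hospital, the effect is nil.

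**4. Small-sample inference at the correct level.** Cluster degrees of freedom: 21 − 3 = 18.

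- Referring the contrast to the normal value: 2 × P(t₁₈ > 2.2414) = 3.8%, against a nominal 2.5%.
- The t₁₈ critical value for two-sided 2.5% is 2.445, so the interval is 2.445 / 2.2414 = 1.09 times as wide.

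**5. Network.** The number of networks is not given. If there are two (an assumption), one further degree of freedom is spent, leaving 17: the normal-based error becomes 3.9% and the critical value 2.458.

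**6. Effect on power under the plan's assumptions.** SE = √[2 × 1.5² × 1.508 / (7 × 26.4)] = 0.192, and 0.6 / 0.192 = 3.13. Normal-based power is Φ(3.13 − 2.24) = 81.3%. With the t₁₈ critical value (noncentral t) it is 74.8%.

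**The case against.** The strongest objection is that there is no mismatch of levels. Section 11.2 equates cluster and hospital, Section 9.1 has 21 hospitals split seven per arm, and Section 8 uses the analysis section's own term for every participant's recruitment site. If units are nested in hospitals and there are 21 of each, the mapping is one-to-one. This stands. The phrase in Section 7.1 about hospitals and health centres describes where care is given and does not establish another trial level.

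A reader might therefore infer from the differing names that the model uses the wrong level and that standard errors will be too small. The documents do not support that inference. The 6.8% figure needs both a hospital covering several randomised units and a model that captures none of the unit variance; the 13.7% also needs an ICC that is not the plan's.

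It can also be said that network and small-sample inference are separate from the naming question. That is correct, and they are argued separately here. Network could enter through the clause on relevant covariates, but that clause is discretionary. The plan expects little variation between networks, so leaving network out is more likely to cost some precision than to inflate error. Nor does the plan say that it will use a normal-based test: it is silent, and the 3.8% applies only if that silence is filled by a large-sample default.

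**Conclusion.** The point holds as a modest, inexpensive improvement to the analysis text.

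- **Cluster name.** Probably inconsistent wording, with no effect on standard errors or on the 693. The residual risk, about 6.8% error at worst with ICC 0.02, is conditional on a structure that the documents do not describe.
- **Minimisation factor.** Its omission is a gap in the stated model. The documents give no figure from which to size its effect.
- **Small-sample inference.** About 3.8% error instead of 2.5%, assuming a normal-based Wald test, a two-sided level and a contrast with 18 cluster degrees of freedom.

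**What to change.** Replace the clustering sentence in Section 10.2.1 with:

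*Each outcome model will include a random intercept for each of the 21 randomised primary care units, a fixed effect for primary care network (the minimisation factor), and a small-sample degrees-of-freedom correction (e.g. Kenward-Roger or Satterthwaite).*

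Define the cluster once, and use that term in Sections 6, 6.1, 8, 9.1, 10.2.1 and 11.2. If a hospital does turn out to cover more than one randomised unit, say so and keep the unit as a random effect.

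The cost is a few words and no new data. Intervals become about 9% wider than normal-based ones, and network uses one degree of freedom if there are two networks. The sponsor should also know that the 81.3% power at 693 rests on the normal approximation. The corrected test has about 74.8% under the same assumptions, because it no longer gains power from an inflated error rate.

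### Baseline adjustment depends on observed imbalance and is optional; the baseline value and the minimisation factor should be fixed in the primary model in advance

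*Combined protocol and SAP*

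**What the plan says.** Section 10.2.1 is the whole quantitative plan. It specifies intention to treat on available outcome data and a model family: "Potential clustering of outcomes at the level of community hospitals will be accounted for using mixed-effects models". On covariates it says only: "Adjustment for baseline imbalances in outcomes or relevant covariates will be considered as appropriate". It sets no threshold for imbalance, gives no list of relevant covariates, and does not say whether the adjusted or the unadjusted estimate is primary. No other section fills these gaps or points to a separate analysis plan.

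Section 4.1.1 defines the first co-primary outcome as "A difference in trial arms at one-year follow-up in HbA1c (co-primary outcome 1") and words the second, total cardiovascular risk, in the same way. Neither definition settles the model.

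The information needed for adjustment is already planned. Section 8 states: "Blood samples will be collected from participants at baseline, 6 and 12 months, to measure Blood glucose, HbA1c and lipids". Section 5 gives the allocation factor: "Randomisation will be minimised by primary care networks to account for any variation in practice, although this is expected to be small".

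**The concern.** The sentence makes imbalance the object of adjustment. The main reason to adjust for a baseline value in a randomised trial is different: it predicts the outcome, so including it removes variance whether or not the arms happen to differ. An analyst could follow section 10.2.1 faithfully and fit an unadjusted model, an adjusted model, or one adjusted only after inspecting the baseline table. The last two are not equivalent, because a conditional rule gives up most of the precision that the baseline measurement could provide.

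With seven units per arm and a small between-unit sample, that precision is worth having. Network is a separate matter. It belongs in the model because allocation used it, not because a precision gain is expected from it.

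**Working it through.** **Inputs from section 9.1:** difference 0.6, SD 1.5, ICC 0.02, 7 clusters per arm, 693 participants, 20% loss, 80% power, 2.5% significance (taken as two-sided, which reproduces the sample size).

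**Assumptions not in the documents:** the correlation r between baseline and 12-month HbA1c (0.3 to 0.7 shown); SD 1.5 is the raw outcome SD; the same SD and ICC hold at baseline; one pairwise comparison of 7 v 7 clusters.

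**1. The plan's own figure.** Per arm without clustering: n = 2(2.2414 + 0.8416)² × 1.5² / 0.6² = 118.8. With 7 clusters, solve 7m = n[1 + (m - 1) × 0.02]: m = 0.98n / (7 - 0.02n) = 25.2, rounded up to 26. Then 26 / 0.8 = 32.5, rounded up to 33, and 33 × 21 = 693. The figure reproduces exactly. It uses no baseline correlation.

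**2. Unadjusted reference.** Analysed per unit: 33 × 0.8 = 26.4. Between-unit variance 0.02 × 2.25 = 0.045; within-unit 2.205. SE = sqrt[2(0.045 + 2.205/26.4)/7] = 0.1916. Power is 81% by the normal approximation and 71.1% on t with 12 df. The t figure is the reference below.

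**3. Never, conditional or always adjusting.** Simulation of cluster means, 400,000 replicates, r = 0.5, baseline explaining both variance components, slope treated as known, t on 12 df. The triggers are assumptions, since section 10.2.1 states none.

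| Rule | How often adjusted | Power |
|---|---|---|
| Never | 0% | 71% |
| If baseline p < 0.05 | 5% | 72% |
| If baseline difference > 0.20 | 30% | 76% |
| Always | 100% | 84% |

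The conditional rules recover little because they seldom act. With no true difference, the imbalance rules reject in 1.3% to 2.5% of trials over the values of r tried, against a nominal 2.5%, so they are conservative.

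**4. The full recommended model.** Baseline and network are each charged one degree of freedom, assuming two networks: 14 - 2 - 2 = 10 df, so the critical value rises from 2.560 to 2.634. The adjusted SE is sqrt[2(B + W/26.4)/7], with W = 2.205(1 - r²) and three choices of B:

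- both components shrink: B = 0.045(1 - r²);
- within-cluster only: B = 0.045;
- cluster-level baseline and outcome unrelated: B = 0.045(1 + r²).

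At r = 0.5 the SEs are 0.1660, 0.1754 and 0.1843.

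| Power on 10 df (change from 71.1%) | r = 0.3 | r = 0.5 | r = 0.7 |
|---|---|---|---|
| Both shrink | 73.2% (+2) | 81.7% (+11) | 94.1% (+23) |
| Within only | 71.6% (+0.5) | 77.0% (+6) | 85.5% (+14) |
| Unrelated at cluster level | 70.1% (-1) | 72.5% (+1) | 76.2% (+5) |

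No figure is possible for total cardiovascular risk, because the documents give no SD for it.

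**The case against.** The best defence is that the plan is not silent. It names imbalance in the outcomes at baseline, which already identifies the baseline value of each outcome as the candidate adjuster, and it fixes the model family, the clustering and the analysis population. That stands, and it narrows the point to the covariate set and the rule for using it.

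It is also fair to say that the gain is uncertain. Every power figure rests on an assumed r, and the recommended model can lose about one point if r is low and cluster-level baseline and outcome are unrelated. Requiring network is partly convention: section 5 itself expects little variation between networks, and no precision gain is claimed here.

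A reader might infer three stronger things, none of which the documents support:

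- **Inflated type I error.** Imbalance-triggered rules are conservative. Inflation would need the estimate to be chosen by its result, which the plan does not propose.
- **A separate harm from conflicting conclusions.** Adjusted and unadjusted results do sometimes fall on opposite sides of the threshold, but this is mostly the power gain counted again. At r = 0.5 with both components shrinking, 15% of trials are significant only when adjusted and 2% only when unadjusted.
- **A wrong sample size.** The 71% reference differs from the stated 80% because it uses t on 12 df. By the normal approximation the design gives 81%, and 693 reproduces.

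**Conclusion.** The point holds as a matter of pre-specification and efficiency. Section 10.2.1 leaves adjustment conditional and optional, although the baseline HbA1c value and the allocation factor will both be available without any new data. Always adjusting is the better rule under most of the assumptions tried. At r = 0.5 with both components shrinking it gives 84% power, against 72% to 76% under an imbalance trigger and 71% unadjusted. After the degrees of freedom of the full model are paid for, the change from unadjusted runs from about -1 to +23 points.

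These sizes are illustrative. They depend on r, on SD 1.5 being raw, on two networks, and on a two-arm comparison. Pooling the third arm would raise the unadjusted reference to 75% on 18 df. The change is worth making, but the plan's validity does not hang on it.

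**What to change.** Replace the adjustment sentence in section 10.2.1 with:

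> The primary model for each co-primary outcome includes arm and the baseline value of that outcome as fixed effects, regardless of observed imbalance, with a random effect for the randomised primary care unit, and primary care network (the minimisation factor) as a fixed effect; the unadjusted estimate is a sensitivity analysis.

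Use one name for the cluster throughout. Section 5 randomises primary care units, while section 10.2.1 places the clustering at community hospitals. For the second co-primary outcome, the sentence can be applied only once the risk score is defined, because no section defines it.

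The cost is wording only. Statistically it is one or two cluster-level degrees of freedom, at about one power point each: at r = 0.5 with both components shrinking, 83.8% on 12 df becomes 82.9% on 11 and 81.7% on 10. If the baseline correlation is low, this can cancel the gain or leave a net loss of about one point. The number of networks should be stated, since section 5 only implies two and more would cost further degrees of freedom.
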